**Table 3: Tabulated overview on data collected during the study**

	Enrollment/ Initial visit	Follow up visit (including end of observation)
Eligibility Assessment (see 9.2.2)	X	
Date	X	X
Demographic data (see 9.3.3)	X	
General medical/surgical history (see 9.3.5)	X	
Disease history (see 9.3.4)	X	
Bleed history (see 9.3.1)	X	
Prior FVIII treatment history (see 9.3.4)	X	
Damoctocog alfa pegol history (if any, see 9.3.7)	X	
Current prescribed damoctocog alfa pegol regimen (see 9.3.7)	X	X
Damoctocog alfa pegol dose/regimen changes, treatment switches (see 9.3.7)		X (Continuous collection)
Patient-Reported Data (Hemo-SAT A, Hemo-QoL-A, Hemo-QoL Short Form, WPAI [+ CIQ: HS]; see 9.3.10)	X	X (Month 12, 24, 36)

	Enrollment/ Initial visit	Follow up visit (including end of observation)
Physical examination (weight, height, vital signs) 	X	X
Joint Health (HJHS)	X	X
Ultrasound data 	X	X
Affected joints	X	X
Damoctocog alfa pegol Pharmacokinetic analysis  (see 9.3.7)	X	X
Concomitant medication (see 9.3.6)	X	X
Adverse events (includes systematically collected AEs and AEs of special interest (see 11)) 	X (Continuous collection)	
Inhibitor 	X	X
Patient infusion diary		X (Continuous collection)
Physician recorded bleeds 		X (Continuous collection)
Physician recorded surgeries		X (Continuous collection)
Reason for end of observation (see 9.3.11)		X (once, at occurrence)

 Routine examinations only, if available.

 PK analysis is at physician's discretion. PK testing (and the frequency of testing per the table) is part of the routine use of the product.

 Adverse events (up to 30 days after the last treatment with damoctocog alfa pegol in study period).

 Serious, life-threatening bleeds and surgery bleeds to be recorded by the physician. Physician to ask patient at each visit regarding bleeds.

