### **9.7.7 Analysis of adverse events**

The analysis described in this section will be performed on incident treatment-emergent adverse events (TEAEs) on the SAF.

An overview table displaying all TEAEs will be presented. This overview table will provide a summary on patient level:

- Any event (AE of special interest, AE, SAE, and AR).
- Maximum intensity of events.
- Events with outcome of death.
- Events leading to change of treatment regimen of study treatment.
- Events leading to discontinuation of study treatment.
- Events related to inhibitor development.

AEs will be coded using the latest version of MedDRA. A summary of TEAEs will be presented by primary System Organ Class (SOC) and Preferred Term (PT). AEs will primarily be classified by MedDRA PT. Aggregate incidences at the SOC level will be presented.

Each of the AEs of special interest will be described separately. Event rates and 95% CIs will be reported as both incidence risks and exposure-adjusted incidence rates.

Additionally, a detailed listing will be provided for AEs related to the development of an inhibitor or positive inhibitor measurements, including information on history of inhibitors.

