An assessment of "no" would include:

- The existence of a clear alternative explanation (e.g., mechanical bleeding at surgical site).
- Non-plausibility (e.g., the patient is struck by an automobile when there is no indication that the product caused disorientation that may have caused the event; cancer developing a few days after the first treatment administration).

An assessment of “yes” indicates that there is a reasonable suspicion that the AE is associated with the use of the study treatment. Factors to be considered in assessing the relationship of the AE to study treatment include:

- The temporal sequence from product administration: The event should occur after the product is given. The length of time from product exposure to event should be evaluated in the clinical context of the event.
- Recovery on product discontinuation (de-challenge), recurrence on product re-introduction (re-challenge): Patient’s response after de-challenge or patient’s response after re-challenge should be considered in the view of the usual clinical course of the event in question.
- Underlying, concomitant, intercurrent diseases: Each event should be evaluated in the context of the natural history and course of the disease being treated and any other disease the patient may have.
- Concomitant medication or treatment: The other products the patient is taking or the treatment the patient receives should be examined to determine whether any of them may be suspected to cause the event in question.
- The pharmacology and PK of the study treatment: The PK properties (absorption, distribution, metabolism and excretion) of the study treatment, coupled with the individual patient’s pharmacodynamics should be considered.

An AE or AR is serious (SAE) if it:

- Results in death.
- Is life-threatening.

- Requires in-patient hospitalization or prolongation of existing hospitalization (see exceptions below).
- Results in persistent or significant disability or incapacity.
- Is a congenital anomaly or birth defect.
- Is medically important.

Death is usually the outcome of an underlying clinical event that causes it. Hence, it is the cause of death that should be regarded as the SAE. The 1 exception to this rule is “sudden death” where no cause has been established. In this instance, “sudden death” should be regarded as the AE and “fatal” as its reason for being “serious”.

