Life-threatening: The term “life-threatening” in the definition of “serious” refers to an AE in which the subject was at risk of death at the time of the event. It does not refer to an AE which hypothetically might have caused death if it were more severe.

Hospitalization: Any AE leading to hospitalization or prolongation of hospitalization will be considered as serious, unless the admission was:

- Planned before patient’s inclusion in the study (i.e., elective or scheduled surgery); or
- Ambulant (shorter than 12 hours); or
- Part of the normal treatment or monitoring of the studied disease (i.e., not due to a worsening of the disease).

However it should be noted that invasive treatment during any hospitalization may fulfill the criteria of “medically important” and as such may be reportable as an SAE dependent on clinical judgment. In addition, where local regulatory authorities specifically require a more stringent definition, the local regulation takes precedent.

Disability means a substantial disruption of a patient’s ability to conduct normal life functions.

Congenital anomaly (birth defect), i.e., any congenital anomaly observed in an infant, or later in a child, should be regarded as an SAE when:

- The mother had been exposed to a medicinal product at any stage during conception or pregnancy or during delivery.
- The father was exposed to a medicinal product prior to conception.

Other medically important serious event: any AEs may be considered serious as it may jeopardize the patient and may require intervention to prevent another serious condition. Medically important events either refer to or might be indicative of a serious disease state. Such reports warrant special attention because of their possible association with serious disease state and may lead to more decisive action than reports on other terms.

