#### AEs of special interest:

The following AEs of special interest are reported (if done in routine clinical practice):

- Hypersensitivity reactions including skin-related and systemic reactions, such as anaphylactic reactions (seriousness should be a case-by-case decision).
- Inhibitor development: inhibitors need to be assessed as mandatory serious and reported to Bayer AG within 24 hours of awareness.
- Loss of drug effect (immune-response to PEG, anti-drug antibodies, etc.).
- Renal impairment.,
- Neurocognitive disorders.,

The reporting physician will be asked to complete additional questionnaires when any of the above AEs of special interest are reported

Any bleeding event occurring during the study will not be documented as an AE, as long as it is not considered to have a "causal relationship" to the product. The events are captured in the assessment of effectiveness. However, if the bleed requires hospitalization, it must be reported as an SAE.

The physician will be asked to document in the eCRF whether the clinical site participates in any registries whereby AEs could be reported to both the registry and the HEM-POWR study.

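### The bleed rule in Section 11.3 excepts only hospitalized bleeds, so for unrelated bleeds that are serious on another criterion it contradicts Sections 11.1 and 11.2

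*Protocol*

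**What the plan says.** The bleed rule stands in Section 11.3, under the events of special interest. It opens with "Any bleeding event occurring during the study will not be documented as an AE, as long as it is not considered"; the test is whether the physician sees a causal link with the product. It then says where the remaining bleeds go: "The events are captured in the assessment of effectiveness". One exception follows: "However, if the bleed requires hospitalization, it must be reported as an SAE".

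Section 11.1 sets the general definitions. An adverse event needs no causal link to treatment. It is serious if it meets any one of six criteria: death, threat to life ("Is life-threatening"), in-patient or prolonged hospitalization, disability, congenital anomaly, or medical importance. For a death, the cause of death is to be treated as the serious event.

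Section 11.2 requires every adverse event, serious or not and related or not, to be documented up to 30 days after the last dose in the observation period. Serious events must be forwarded within one business day of awareness.

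Table 3, footnote 4, adds: "Serious, life-threatening bleeds and surgery bleeds to be recorded by the physician". Section 9.3.2 repeats this in its list of effectiveness variables. Section 9.7.7 plans a patient-level overview of treatment-emergent adverse events, with serious events included and a separate row for "Events with outcome of death".

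**The concern.** Treating breakthrough bleeds as effectiveness outcomes rather than adverse events is a reasonable choice in hemophilia. The fault is in how the rule returns the worst bleeds to safety reporting: it carries over hospitalization and none of the other seriousness criteria. A patient who dies of a bleed at home, or survives a life-threatening bleed without admission, falls outside the exception if the physician answers the causality question with no.

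At stake are prompt notice to the marketing authorization holder and the completeness of the safety tables in a post-authorization safety study whose secondary objectives include long-term safety. An analysis plan cannot repair this later, because it cannot tabulate as an adverse event what sites were told not to document as one.

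**Working it through.** No figure is involved, so the check is to apply each section to the same event. Take a bleed that is judged unrelated, does not lead to hospitalization, and is fatal or life-threatening.

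| Question | Section 11.3, bleed rule | Sections 11.1 and 11.2 |
|---|---|---|
| Is it an adverse event? | No, because it is not judged related | Yes, because causality is not required |
| Is it serious? | The one exception, hospitalization, is not met | Yes, on the death or life-threatening criterion |
| Must it be documented as an AE or SAE? | No; it is captured under effectiveness | Yes, whatever the relationship |
| Is it forwarded within one business day? | No | Yes |

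The answers are opposite in every row.

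**Which criteria are affected.** Section 11.1 lists six. Hospitalization is covered by the exception. Congenital anomaly has no practical bearing on a patient's own bleed. That leaves 6 − 1 − 1 = 4 criteria on which an unrelated bleed could be serious and still fall outside the rule: death, threat to life, disability and medical importance.

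**How far the hospitalization exception reaches.** Section 11.1 does not count an ambulant admission of under 12 hours as serious hospitalization. If that definition governs the bleed rule, a life-threatening bleed managed in a short stay also falls outside the exception. Section 11.3 does not say whether it does.

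**Whether another section closes the gap.**

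1. Table 3 and Section 9.3.2 have the physician record serious and life-threatening bleeds. This shows that the protocol expects such bleeds as a category of their own. Neither place links them to reporting as serious adverse events, and Section 9.3.2 lists them under effectiveness.
2. Section 11.1 counts lack of drug effect as an adverse event. Nothing tells the physician to use that route for a fatal or life-threatening bleed, and the more specific bleed rule points the other way.
3. The paragraph on serious events in Section 11.3 acts only on events already entered as serious.
4. Section 11.1 gives mechanical bleeding at a surgical site as an example of an adverse event with no causal relationship. The definitions therefore already treat an unrelated bleed as an adverse event.

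None of these resolves the conflict, and the fourth sharpens it.

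**The case against.** The strongest reply is that these bleeds are not lost. The physician records them as bleeds, and death is a named reason for end of observation in Section 9.2.7, collected under Table 3. Training and medical review under Section 9.8.1 might also catch a misfiled case. The first two points stand and limit the consequence to routing and tabulation. The third is possible, but the protocol does not say that either measure addresses this conflict.

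A reader might also infer more than the documents support:

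- *That only hospitalized bleeds can ever be serious adverse events.* A bleed judged related remains an adverse event, and every criterion in Section 11.1 applies to it.
- *That deaths would vanish, with a calculable error in mortality.* A fatal bleed would normally still be visible in patient disposition. What is lost is its entry in the fatal-event row. Mortality is not a named endpoint, and Table 5 concerns the chance of observing events, so it cannot size a misfiled death.
- *That authorities would miss expedited reports.* Section 11.3 has the marketing authorization holder submit serious events related to the product. The bleeds at issue are judged unrelated, so that sentence would not send them on even if they were filed as serious.
- *That signals of inhibitors or loss of drug effect would go unreported.* Both are reportable events of special interest in their own right, and inhibitors must be reported within 24 hours. That route depends on the physician suspecting one of them, so it narrows the gap without closing it.
- *That Table 3 sends these bleeds to a form without prompt reporting.* The footnote names no form, and the case report form is a stand-alone document that is not available here.

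**Conclusion.** The contradiction is real and confined to one intersection: bleeds judged unrelated, not hospitalized, and serious on another criterion. For these, Section 11.3 as written removes the one-business-day forwarding to the marketing authorization holder and the entry in the serious and fatal rows of the Section 9.7.7 overview.

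The documents give no rate for such bleeds, so no number can be put on the loss. Few are expected. The primary analysis of annualized bleeding rate is unaffected, because the bleeds are still counted there. The point deserves correction because the few events concerned are the gravest ones, the gate is a single yes-or-no causality judgment, and sites could reasonably follow either section. The conclusion assumes that sites apply the specific bleed rule over the general definitions, and that no stand-alone document tells them otherwise.

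**What to change.** Reconcile the bleed rule in Section 11.3 with Sections 11.1 and 11.2. Replace the hospitalization condition with one that covers a bleed meeting any seriousness criterion of Section 11.1. Add that such a bleed is recorded both as an effectiveness event and as a serious adverse event, and that it counts in the tables of Section 9.7.7, including the fatal-event row. A cross-reference from Table 3, footnote 4, would help sites apply it.

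The cost is one or two sentences, matching guidance to sites and in the electronic case report form, and a few more serious adverse event reports. No treatment and no effectiveness endpoint changes.

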## **11.4 Evaluation**

Whenever new important safety information is received, e.g., case reports from a physician, the reports are processed and entered into the global pharmacovigilance safety database. These reports will be reviewed on a regular basis (for information on collection, management and reporting of case reports, refer to Sections 11.2 and 11.3). If a potential safety signal is suspected, an investigation of the suspected potential signal will be performed according to internal standard operating procedures, for further evaluation within the context of benefit-risk.

## **12. Plans for disseminating and communicating study results**

This study will be registered at "www.clinicaltrials.gov" and in the EU PAS register at "http://www.encepp.eu/encepp\_studies/indexRegister.shtml". Results will be disclosed in a publicly available database within the standard timelines.

If a regulatory authority requests progress reports these will be provided in agreed frequency and content.

The results of this OS are intended to be published in a peer-reviewed journal and as abstracts/presentations at medical congresses under the oversight of the MAH. Current guidelines and recommendation on Good Publication Practice (GPP) will be followed (e.g., GPP 2 guidelines [38], Strengthening the Reporting of Observational Studies in Epidemiology [STROBE] [39]). No individual physician may publish the results of this study, or their own patients, without prior approval from the MAH.

## Annex 1: List of stand-alone documents

**Table 6: List of stand-alone documents**

Document Name	Final version and date (if available)*
<Physician list>	tbd
<Country & Site list>	tbd
<Steering/Publication Committee Members>	tbd
<Steering/Publication Committee Charter>	v 0.1, 17 OCT 2018 <draft>
<Study timelines and milestone update>	tbd
<CRF>	v 2.0, 04 MAR 2019
<EDC System>	tbd
<EDC System Validation>	tbd
<DMP>	tbd
<SAP>	tbd
<MRP>	tbd
<QRP>	tbd
<Description of data quality improvement measures>	tbd

\* Draft versions are indicated by <draft> in brackets and date. “tbd” indicates documents that are not available at the time of protocol creation, but will be issued at a later stage

## Annex 2: ENCePP checklist for post-authorization safety study (PASS) protocols

**Study title:** HEM-POWR: Observational Study Evaluating Effectiveness and Safety of Real-World Treatment with Damoctocog alfa pegol in Previously Treated Patients with Hemophilia A

**EU PAS Register® number:**  
**Study reference number (if applicable):** n/a

Section 1: Milestones	Yes	No	N/A	Section Number
1.1 Does the protocol specify timelines for				
1.1.1 Start of data collection 				6
1.1.2 End of data collection 				6
1.1.3 Progress report(s)				6
1.1.4 Interim report(s)				6
1.1.5 Registration in the EU PAS Register®				6
1.1.6 Final report of study results.				6

Comments:

Section 2: Research question	Yes	No	N/A	Section Number
2.1 Does the formulation of the research question and objectives clearly explain:				7,8,9
2.1.1 Why the study is conducted? (e.g. to address an important public health concern, a risk identified in the risk management plan, an emerging safety issue)				7
2.1.2 The objective(s) of the study?				8
2.1.3 The target population? (i.e. population or subgroup to whom the study results are intended to be generalised)				9
2.1.4 Which hypothesis(-es) is (are) to be tested?				
2.1.5 If applicable, that there is no a priori hypothesis?				9.7.1

Comments:

This is a prospective, observational study, so no hypothesis is being tested.

 Date from which information on the first study is first recorded in the study dataset or, in the case of secondary use of data, the date from which data extraction starts.

 Date from which the analytical dataset is completely available.

Section 3: Study design		Yes	No	N/A	Section Number
3.1	Is the study design described? (e.g. cohort, case-control, cross-sectional, other design)				9.1
3.2	Does the protocol specify whether the study is based on primary, secondary or combined data collection?				9.1
3.3	Does the protocol specify measures of occurrence? (e.g., rate, risk, prevalence)				9.7.1
3.4	Does the protocol specify measure(s) of association? (e.g. risk, odds ratio, excess risk, rate ratio, hazard ratio, risk/rate difference, number needed to harm (NNH))				
3.5	Does the protocol describe the approach for the collection and reporting of adverse events/adverse reactions? (e.g. adverse events that will not be collected in case of primary data collection)				11.2, 11.3

Comments:

Statistical analyses will be descriptive and explorative in nature.

Section 4: Source and study populations		Yes	No	N/A	Section Number
4.1	Is the source population described?				9.1
4.2	Is the planned study population defined in terms of:				
	4.2.1 Study time period				9.1
	4.2.2 Age and sex				9.1
	4.2.3 Country of origin				9.1
	4.2.4 Disease/indication				9.1
	4.2.5 Duration of follow-up				9.1
4.3	Does the protocol define how the study population will be sampled from the source population? (e.g. event or inclusion/exclusion criteria)				9.2.1

Comments:

Section 5: Exposure definition and measurement		Yes	No	N/A	Section Number
5.1	Does the protocol describe how the study exposure is defined and measured? (e.g. operational details for defining and categorising exposure, measurement of dose and duration of drug exposure)				9.3.7
5.2	Does the protocol address the validity of the exposure measurement? (e.g. precision, accuracy, use of validation sub-study)				9.3.7
5.3	Is exposure categorised according to time windows?				
5.4	Is intensity of exposure addressed? (e.g. dose, duration)				

Section 5: Exposure definition and measurement	Yes	No	N/A	Section Number
5.5 Is exposure categorised based on biological mechanism of action and taking into account the pharmacokinetics and pharmacodynamics of the drug?				
5.6 Is (are) (an) appropriate comparator(s) identified?				

Comments:

This is a non-interventional study, and all treatment decisions (including dosing and exposure) will be made by the treating physician without influence from the sponsor. Study is without comparator. Study is without comparator.

Section 6: Outcome definition and measurement	Yes	No	N/A	Section Number
6.1 Does the protocol specify the primary and secondary (if applicable) outcome(s) to be investigated?				9.1
6.2 Does the protocol describe how the outcomes are defined and measured?				9.1, 9.3.1, 9.3.2
6.3 Does the protocol address the validity of outcome measurement? (e.g. precision, accuracy, sensitivity, specificity, positive predictive value, use of validation sub-study)				9.3.7
6.4 Does the protocol describe specific outcomes relevant for Health Technology Assessment? (e.g. HRQoL, QALYs, DALYs, health care services utilisation, burden of disease or treatment, compliance, disease management)				9.3.9

Comments:

Section 7: Bias	Yes	No	N/A	Section Number
7.1 Does the protocol address ways to measure confounding? (e.g. confounding by indication)				9.7.1
7.2 Does the protocol address selection bias? (e.g. healthy user/adherer bias)				9.9
7.3 Does the protocol address information bias? (e.g. misclassification of exposure and outcomes, time-related bias)				9.9

Comments:

Section 8: Effect measure modification	Yes	No	N/A	Section Number
--	------------	-----------	------------	-----------------------

Section 8: Effect measure modification	Yes	No	N/A	Section Number
8.1 Does the protocol address effect modifiers? (e.g. collection of data on known effect modifiers, sub-group analyses, anticipated direction of effect)				9.7.1

Comments:

Section 9: Data sources	Yes	No	N/A	Section Number
9.1 Does the protocol describe the data source(s) used in the study for the ascertainment of:				
9.1.1 Exposure? (e.g. pharmacy dispensing, general practice prescribing, claims data, self-report, face-to-face interview)				9.4
9.1.2 Outcomes? (e.g. clinical records, laboratory markers or values, claims data, self-report, patient interview including scales and questionnaires, vital statistics)				9.4
9.1.3 Covariates and other characteristics?				9.3
9.2 Does the protocol describe the information available from the data source(s) on:				
9.2.1 Exposure? (e.g. date of dispensing, drug quantity, dose, number of days of supply prescription, daily dosage, prescriber)				9.4
9.2.2 Outcomes? (e.g. date of occurrence, multiple event, severity measures related to event)				9.4
9.2.3 Covariates and other characteristics? (e.g. age, sex, clinical and drug use history, co-morbidity, co-medications, lifestyle)				9.4
9.3 Is a coding system described for:				
9.3.1 Exposure? (e.g. WHO Drug Dictionary, Anatomical Therapeutic Chemical (ATC) Classification System)				9.7
9.3.2 Outcomes? (e.g. International Classification of Diseases (ICD), Medical Dictionary for Regulatory Activities (MedDRA))				9.7
9.3.3 Covariates and other characteristics?				9.7
9.4 Is a linkage method between data sources described? (e.g. based on a unique identifier or other)				9.8

Comments:

Section 10: Analysis plan	Yes	No	N/A	Section Number
10.1 Are the statistical methods and the reason for their choice described?				9.7
10.2 Is study size and/or statistical precision estimated?				9.5
10.3 Are descriptive analyses included?				9.7
10.4 Are stratified analyses included?				9.7

Section 10: Analysis plan	Yes	No	N/A	Section Number
10.5 Does the plan describe methods for analytic control of confounding?				9.7
10.6 Does the plan describe methods for analytic control of outcome misclassification?				
10.7 Does the plan describe methods for handling missing data?				9.7
10.8 Are relevant sensitivity analyses described?				

Comments:

Outcome depends on quality of patient diary.  
 No comparisons will be made.

Section 11: Data management and quality control	Yes	No	N/A	Section Number
11.1 Does the protocol provide information on data storage? (e.g. software and IT environment, database maintenance and anti-fraud protection, archiving)				9.6
11.2 Are methods of quality assurance described?				9.8
11.3 Is there a system in place for independent review of study results?				9.8

Comments:

Section 12: Limitations	Yes	No	N/A	Section Number
12.1 Does the protocol discuss the impact on the study results of:				
12.1.1 Selection bias?				9.7
12.1.2 Information bias?				9.7
12.1.3 Residual/unmeasured confounding? (e.g. anticipated direction and magnitude of such biases, validation sub-study, use of validation and external data, analytical methods).				9.7
12.2 Does the protocol discuss study feasibility? (e.g. study size, anticipated exposure uptake, duration of follow-up in a cohort study, patient recruitment, precision of the estimates)				9.5

Comments:

Section 13: Ethical/data protection issues	Yes	No	N/A	Section Number
13.1 Have requirements of Ethics Committee/ Institutional Review Board been described?				10.3

Section 13: Ethical/data protection issues	Yes	No	N/A	Section Number
13.2 Has any outcome of an ethical review procedure been addressed?				
13.3 Have data protection requirements been described?				10.6

Comments:

No relevant outcomes of an ethical review procedure are necessary for inclusion.

Section 14: Amendments and deviations	Yes	No	N/A	Section Number
14.1 Does the protocol include a section to document amendments and deviations?				5

Comments:

Section 15: Plans for communication of study results	Yes	No	N/A	Section Number
15.1 Are plans described for communicating study results (e.g. to regulatory authorities)?				12
15.2 Are plans described for disseminating study results externally, including publication?				12

Comments:

Name of the main author of the protocol: PPD \_\_\_\_\_

Date: dd/M/yyyy, 25/03/2019

Signature: \_\_\_\_\_

Note: ENCeP \_\_\_\_\_ protocols (Revision 4, adopted by ENCePP on 15/10/2018)

